11.1 SAFETY MONITORING

Subjects will be evaluated for occurrence of AEs at each visit. Events will be characterized and reported as described below. Safety will also be monitored by performing physical exams and routine laboratory procedures.

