11.1.1 Adverse Events and Serious Adverse Events

Definitions of AEs, non-serious AE, and serious adverse events (SAEs) are provided in this section. Additionally, provided in the sections below are reporting guidelines for any AE or SAE occurring during this study.

Definition of Adverse Event and Non-Serious Adverse Event

The following definition of AE will be used for the study: "Any untoward medical occurrence in a subject or clinical investigation subject administered a pharmaceutical product and which does not necessarily have to have a causal relationship with this treatment. An adverse event can therefore be any unfavorable and unintended sign (including an abnormal laboratory finding), symptom, or disease temporally associated with the use of a medicinal (investigational) product, whether or not related to medicinal (investigational) product."

This definition includes any abnormalities or anomalies that were not seen at baseline or which worsened during the course of the study, if present at baseline.

A "non-serious" adverse event is any event that does not meet the definition of "serious adverse event" as presented, below.

Reporting and Treating Non-Serious Events

It is the responsibility of the investigator to perform regular assessments for AEs. Subjects will be regularly queried about the occurrence of any AEs and will be monitored throughout the

study for reactions to study drug and/or study procedures. The investigator and clinical staff will record all AEs, whether volunteered by or elicited from the subject, at any time during a subject"s participation in the study. Abnormal laboratory findings (e.g., hematology, comprehensive metabolic panel) or other abnormal assessments (e.g., vital signs) will be recorded as AEs if they are judged as clinically significant by the investigator.

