The severity of all adverse events should be graded according to the Common Terminology Criteria for Adverse Events (CTCAE) V4.0. For those adverse events not listed in the CTCAE, the following grading system should be employed:

- ➤ *Mild* (CTCAE Grade 1): Transient symptoms, awareness of sign/symptom, but easily tolerated and no interference with subject"s daily activities
- Moderate (CTCAE Grade 2): Marked signs/symptoms that interfere with subject susual activities, but still acceptable
- > Severe (CTCAE Grade 3): Incapacitating signs/symptoms which cause considerable interference with the subject saily activities, unacceptable
- ➤ Life-threatening (CTCAE Grade 4): Life-threatening of disabling AE
- ➤ Death (CTCAE Grade 5): Death-related AE. See CTCAE Guidelines for assigning Grade 5.

Definition of Serious Adverse Event

The following definition of SAE applies for the study: "A serious AE means any AE occurring at any dose that results in any of the following outcomes: death, a life-threatening AE, inpatient hospitalization or prolongation of existing hospitalization, a persistent or significant disability/incapacity, a congenital anomaly/birth defect, or overdose of study drug. Important medical events that may not result in death, be life threatening, or require hospitalization may be considered a serious AE when, based upon appropriate medical judgment, they may jeopardize the subject or subject and may require medical or surgical intervention to prevent one of the outcomes listed in this definition. A life-threatening AE is any AE that places the subject or subject, in the view of the investigator, at immediate risk of death from the reaction as it occurred (e.g., it does not include a reaction that, had it occurred in a more severe form, might have caused death)." Reporting and Treating Serious Adverse Events as per section 17.2.

Pregnancies

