The ORR is defined as the proportion of subjects CR or PR based on RECIST criteria. The exact 95% CI of ORR will be estimated using the binomial distribution. Progression-free survival will be measured from the start of treatment with pembrolizumab until the documentation of disease progression or death due to any cause, whichever occurs first. Progression-free survival will be censored on the date of last tumor assessment documenting absence of tumor progression for subjects who are still alive prior to data cutoff, dropout, or the initiation of alternate anticancer treatment. Subjects having no tumor assessments after the start of treatment with pembrolizumab will have PFS censored on the first date of treatment with pembrolizumab. Progression-free survival will be evaluated using the Kaplan-Meier method (Kaplan and Meier, 1958). Overall survival will be determined as the time from the start of

treatment with pembrolizumab until death. For subjects who are alive at the end of study or lost to follow-up, OS will be censored on the last date when subjects are known to be alive. The OS will be evaluated using the Kaplan-Meier method.

Safety and Tolerability Analyses

All recorded adverse events will be listed and tabulated by system organ class, preferred term and treatment. Any significant vital signs and clinical laboratory test results will be listed and summarized. Any significant physical examination findings, and clinical laboratory results will be listed.

Biomarker Analysis

Exploratory research studies will be done to evaluate the effect of this therapy will be performed using research blood draws and tumor biopsies at baseline, 1 week after completing RT or undergoing ablation (from the radiated/ablated lesion), and then 4 weeks after dose #1 of pembrolizumab (from a non-radiated/ablated lesion).

The pharmacodynamic effect of pembrolizumab and RT or ablation on Tumor Infiltrating Lymphocytes (TILs), such as CD4+ and CD8+ T-cells, and expression of tumor markers, such as PD-L1, will be assessed by summary statistics, and investigated graphically to explore patterns of change from pre-treatment to post-treatment specimens.

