A copy of all 15 Day Reports and Annual Progress Reports is submitted as required by FDA, European Union (EU), Pharmaceutical and Medical Devices agency (PMDA) or other local regulators. Investigators will cross reference this submission according to local regulations to the Merck Investigational Compound Number (IND, CSA, etc.) at the time of submission. Additionally investigators will submit a copy of these reports to Merck & Co., Inc. (Attn: Worldwide Product Safety; [contact]) at the time of submission to FDA.

All subjects with serious adverse events must be followed up for outcome.

Events of Clinical Interest

Selected non-serious and serious adverse events are also known as Events of Clinical Interest (ECI) (see APPENDIX C) and must be recorded as such on the Adverse Event case report forms/worksheets and reported within 5 calendar days to the MSKCC Safety Office and to Merck Global Safety. (Attn: Worldwide Product Safety; [contact]) according to the ECI reporting guidance (APPENDIX C).

Events of clinical interest for this trial include:

- 1. an overdose of Merck product, as defined in Section 11.1.3 Definition of an Overdose for This Protocol and Reporting of Overdose to the Sponsor, that is not associated with clinical symptoms or abnormal laboratory results.
- 2. an elevated AST or ALT lab value that is greater than or equal to 3X the upper limit of normal and an elevated total bilirubin lab value that is greater than or equal to 2X the upper limit of normal and, at the same time, an alkaline phosphatase lab value that is less than 2X the upper limit of normal, as determined by way of protocol-specified laboratory testing or unscheduled laboratory testing.
- **Note: These criteria are based upon available regulatory guidance documents. The purpose of the criteria is to specify a threshold of abnormal hepatic tests that may require an additional evaluation for an underlying etiology. The trial site guidance for assessment and follow up of these criteria can be found in the Investigator Trial File Binder (or equivalent).
- 3. In the event a subject develops any of the following AEs, a detailed narrative of the event should be reported as an ECI to the Sponsor within 5 calendar days to the

MSKCC Safety Office and to Merck Global Safety according to the ECI reporting guidance (APPENDIX C):

- a. Grade ≥ 3 diarrhea
- b. Grade ≥ 3 colitis
- c. Grade ≥ 2 pneumonitis
- d. Grade ≥ 3 hypo- or hyperthyroidism

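### The laboratory and vital-sign summary covers only results called significant, which is undefined, so changes outside the stated liver and thyroid limits can be missing from both that summary and the adverse event tables.

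*Combined protocol and SAP*

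**What the plan says.** The safety paragraph of Section 14.0 has three relevant sentences.

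- Adverse events: "All recorded adverse events will be listed and tabulated by system organ class, preferred term and treatment".
- Laboratory and vital signs: "Any significant vital signs and clinical laboratory test results will be listed and summarized".
- A closing sentence: "Any significant physical examination findings, and clinical laboratory results will be listed".

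None of them defines *significant*, by number or by grade, or names the person who decides.

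Section 11.1.1 governs which laboratory and vital-sign abnormalities become AEs. They "will be recorded as AEs if they are judged as clinically significant by the investigator". The AE definition in the same section is wider: "This definition includes any abnormalities or anomalies that were not seen at baseline or which worsened during the course of the study". CTCAE is adopted, but for events already recorded as AEs: "The severity of all adverse events should be graded according to the Common Terminology Criteria for Adverse Events (CTCAE) V4.0".

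The Study Calendar in Section 10.0 schedules a blood count and metabolic panel about every 3 weeks. Thyroid tests are at screening, weeks 6 and 12, then odd cycles. Vital signs are taken at every treatment visit. Section 11.1 makes these tests part of safety monitoring: "Safety will also be monitored by performing physical exams and routine laboratory procedures". Safety and tolerability is the first secondary objective in Section 2.0.

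**The concern.** The second Section 14.0 sentence is a selection rule: it says which results enter the summary. A summary restricted in this way reports how often someone called a result significant, not how often the abnormality occurred. The AE tables would normally fill the gap, but they take in laboratory and vital-sign changes through a similar judgement. If both filters turn on the same view of a result, a gradable change can pass through the trial without being counted in either table.

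What is at stake is the reported incidence of laboratory abnormalities under the combination. Omission can only move that incidence down.

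**Working it through.** The plan states no figure on this point to reproduce. The check is to follow a scheduled result through each route into the reported safety results.

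**Route 1: laboratory and vital-sign summary (Section 14.0).** Entry requires *significant*, which is undefined. No section plans a summary of all scheduled values.

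**Route 2: AE tables (Sections 11.1.1 and 14.0).** Only recorded AEs are tabulated, and an abnormal value is recorded only if judged clinically significant. A value that is new or worse than baseline meets the AE definition, yet the recording rule lets it go unrecorded.

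**Route 3: fixed limits that do not use the word *significant*.**

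- Section 17.2, Events of Clinical Interest (ECIs), item 2: "an elevated AST or ALT lab value that is greater than or equal to 3X the upper limit of normal", together with total bilirubin of at least 2 times the upper limit of normal (ULN) and alkaline phosphatase below 2 times ULN. All three are required.
- Section 11.1.3, hepatic function abnormality: ALT or AST above 3 times ULN with bilirubin above 2 times ULN. Such an event may still go unrecorded if it is put down to a pre-existing condition that has not worsened, or to normal fluctuation.
- Section 17.2, ECI item 3d: Grade 3 or higher hypo- or hyperthyroidism.

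ECIs must be entered on the AE forms, so they reach the AE tables.

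**What remains.** Blood counts, creatinine, electrolytes, AST or ALT rises without the bilirubin rise, thyroid changes below Grade 3, and vital signs have no limit in the text available. For these, a result judged not significant has no route into a table.

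**Route 4: listing.** The closing sentence can be read in two ways. If *significant* governs both of its items, it adds nothing for laboratory results. If it governs only the physical findings, all laboratory results are listed. Even then there is no count, rate or grade, and vital signs are not mentioned.

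**Size.** The full cohort is 24 treated subjects and stage 1 is 9 (Section 14.0).

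- One omitted subject: 1/24 = 4.2 points in a full cohort; 1/9 = 11.1 points in a cohort stopped at stage 1.
- Let p be the true proportion of subjects with an abnormality and q the fraction of them called significant. Expected number missed = 24 × p × (1 − q). The documents give neither p nor q, so these are assumed ranges:

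| p | q = 0.50 | q = 0.75 | q = 1 |
|---|---|---|---|
| 10% (2.4 affected) | 1.2 missed | 0.6 missed | 0 |
| 20% (4.8 affected) | 2.4 missed | 1.2 missed | 0 |
| 30% (7.2 affected) | 3.6 missed | 1.8 missed | 0 |

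- Chance that a cohort of 24 reports no case at all = (1 − p × q)^24. At p = 10% this is 0.080 with full counting and 0.292 with q = 0.50.

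**The case against.** The strongest reply is that this is one undefined word in a descriptive analysis of a secondary objective, in a single-centre study of 18 to 48 subjects. The serious laboratory signals have fixed limits. Section 17.2 also asks for laboratory results to be reviewed for possible ECIs before each dose and refers to further ECIs in a guidance document (Appendix C). That document's text is not available here, so other limits may exist. A one-line definition of *significant* would make the rule reproducible.

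Much of this stands. The point is confined to changes outside the visible limits, and no decision rule uses the laboratory summaries. But a definition alone would still leave results below it out of the summary, although the tests are scheduled for every subject.

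Several stronger readings are tempting and are not supported:

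- *A transaminase rise blamed on liver metastases or ablation drops out.* Section 11.1.1 defines AEs regardless of relationship to the drug and rates relationship separately. Section 11.1.3 says an established unrelated diagnosis should be recorded. The filter is significance, not attribution.
- *Only the combined liver criterion escapes judgement.* Grade 3 or higher thyroid events are also ECIs.
- *Such toxicity necessarily vanishes from all safety output.* All laboratory results may be listed, depending on how the closing sentence is read.
- *Unblinded investigators bias the result.* Section 14.0 names no assessor, and a single-arm study has no allocation to conceal.
- *The comparison between cohorts is invalid.* Toxicity is to be summarised by cohort; no safety comparison between cohorts is planned.

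**Conclusion.** The point holds in a limited form. As written, the plan allows laboratory and vital-sign changes outside the visible liver and thyroid limits to be missing from both the laboratory summary and the AE tables. For laboratory results, a listing is the most that may remain. The incidence of laboratory abnormalities would then be understated, by an amount the documents do not allow anyone to estimate; the ranges shown rest on assumed rates.

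The conclusion assumes that a result judged not significant for one output is judged the same way for the other. It also takes the quantity of interest to be the proportion of subjects with a gradable change. The primary endpoint, the two-stage decision rules and the error rates are untouched. This should be changed because the better method is cheap, not because the trial's main conclusion is at risk.

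**What to change.** Replace the laboratory sentence in Section 14.0 with wording such as: All scheduled post-baseline blood count, metabolic panel and thyroid results will be graded from the numeric value, using CTCAE v4.0 where a grade exists and otherwise below, within or above the normal range. Worst post-baseline grade will be tabulated against baseline grade by cohort, for all treated subjects with data, regardless of judged significance.

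Tabulating against baseline matters because Table 6.1 admits subjects with liver metastases and AST or ALT up to 5 times ULN, so a worst grade alone would mix entry status with change on treatment. Keep the listing of significant findings as a supplement. State whether the closing sentence lists all laboratory results. For vital signs, give a numeric definition of *significant* or summarise change from baseline. Align the AE recording rule in Section 11.1.1 with the AE definition there.

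The cost is a few extra tables and no new tests. Section 16.0 does not say which laboratory values are entered in the database, so some extra data extraction may be needed. The reported laboratory toxicity may look slightly less favourable.

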15.0 RESEARCH PARTICIPANT REGISTRATION AND RANDOMIZATION PROCEDURES

15.1 Research Participant Registration

Confirm eligibility as defined in the section entitled Criteria for Patient/Subject Eligibility.

Obtain informed consent, by following procedures defined in section entitled Informed Consent Procedures.

During the registration process registering individuals will be required to complete a protocol specific Eligibility Checklist.

All participants must be registered through the Protocol Participant Registration (PPR) Office at Memorial Sloan-Kettering Cancer Center. PPR is available Monday through Friday from 8:30am – 5:30pm at [contact]. Registrations must be submitted via the PPR Electronic Registration System (http://ppr/). The completed signature page of the written consent/RA or verbal script/RA, a completed Eligibility Checklist and other relevant documents must be uploaded via the PPR Electronic Registration System.

15.2 Randomization

n/a

16.0 DATAMANAGEMENTISSUES

A Research Study Assistant (RSA) will be assigned to the study. The responsibilities of the RSA include project compliance, data collection, abstraction and entry, data reporting, regulatory monitoring, problem resolution and prioritization, and coordinate the activities of the protocol study team.

The data collected for this study will be entered into a secured database (Clinical Research Database, CRDB) at Memorial Sloan-Kettering Cancer Center. Source documentation will be available to support the computerized patient record.

16.1 Quality Assurance

Weekly registration reports will be generated to monitor patient accruals and completeness of registration data. Routine data quality reports will be generated to assess missing data and inconsistencies. Accrual rates and extent and accuracy of evaluations and follow-up will be monitored periodically throughout the study period and potential problems will be brought to the attention of the study team for discussion and action. Random-sample data quality and protocol compliance audits may be conducted by the study team, at a minimum of two times per year, more frequently if indicated.

16.2 Data and Safety Monitoring

The Data and Safety Monitoring (DSM) Plans at Memorial Sloan-Kettering Cancer Center were approved by the National Cancer Institute in September 2001. The plans address the new policies set forth by the NCI in the document entitled "Policy of the National Cancer Institute for Data and Safety Monitoring of Clinical Trials", which can be found at http://cancertrials.nci.nih.gov/researchers/dsm/index.html. The DSM Plans at MSKCC were established and are monitored by the Office of Clinical Research. The MSKCC DSM Plans can be found on the MSKCC Intranet at http://mskweb5.mskcc.org/intranet/ assets/ tables/content/359689/Data safety%20Mon http://mskweb5.mskcc.org/intranet/ assets/ tables/content/359689/Data safety%20Mon

17.0 PROTECTION OF HUMAN SUBJECTS

Participation in this trial is voluntary. All patients will be required to sign a statement of informed consent, which must conform to IRB guidelines.

Inclusion of Women and Minorities: Memorial Sloan-Kettering Cancer Center has filed forms HHS 441 (civil rights), HHS (handicapped individual), 639-A (sex discrimination), and 680 (age discrimination); we also take due notice of the NIH policy concerning inclusion of women and minorities in clinical research populations. Patients of all races, both male and female, will be accepted into the protocol. The proposed study population is as described in section 7.0.

Exclusion of Lactating or Pregnant Women: Children have been excluded from this study. Colorectal adenocarcinoma is an adult cancer. Thus, the relevance of these drug to the pediatric population has not been established. Lactating and pregnant women are also excluded because of potential anti-proliferative effects of chemotherapy that may be harmful to the developing fetus or nursing infant.

Benefits: It is possible that this treatment will result in shrinkage of colorectal cancer or in a stabilization of an otherwise progressing disease. It is not known, of course, whether these or any other favorable events will occur. It is not known whether this treatment will affect the overall survival of the patients.

Costs: The patient will be responsible for the costs of standard medical care, including, CT scans, all drug administration fees and all hospitalizations, even for complications of treatment. Pembrolizumab will be supplied to patients by Merck at no cost. Patients will not be responsible for the costs of blood procurement obtained for research purposes, the cost of special testing of any tissue for research purposes, or the cost for obtaining the tumor biopsy for research purposes.

Incentives: No incentives will be offered to patients/subjects for participation in the study.

Alternatives: Patients may be eligible for other investigational studies, or focus on palliative care options.

Confidentiality: Every effort will be made to maintain patient confidentiality. Research and hospital records are confidential. Patient"s name or any other personally identifying information will not be used in reports or publications resulting from this study. The Food and Drug Administration or other authorized agencies (e.g., qualified monitors) may review patients records and pathology slides, as required.

17.1 Privacy

MSKCC"s Privacy Office may allow the use and disclosure of protected health information pursuant to a completed and signed Research Authorization form. The use and disclosure of protected health information will be limited to the individuals described in the Research Authorization form. A Research Authorization form must be completed by the Principal Investigator and approved by the IRB and Privacy Board (IRB/PB).

17.2 Serious Adverse Event (SAE) Reporting

Any SAE must be reported to the IRB/PB as soon as possible but no later than 5 calendar days. The IRB/PB requires a Clinical Research Database (CRDB) SAE report be submitted electronically to the SAE Office at [contact]. The report should contain the following information:

Fields populated from CRDB:

- Subject"s name (generate the report with only initials if it will be sent outside of MSKCC)
- Medical record number
- Disease/histology (if applicable)
- Protocol number and title

Data needing to be entered:

- The date the adverse event occurred
- The adverse event
- Relationship of the adverse event to the treatment (drug, device, or intervention)
- If the AE was expected
- The severity of the AE
- The intervention
- Detailed text that includes the following
 - A explanation of how the AE was handled
 - A description of the subject"s condition
 - Indication if the subject remains on the study
 - If an amendment will need to be made to the protocol and/or consent form.

The PI's signature and the date it was signed are required on the completed report.

For IND/IDE protocols: The CRDB AE report should be completed as above and the FDA assigned IND/IDE number written at the top of the report. If appropriate, the report will be forwarded to the FDA by the SAE staff through the IND Office.

17.2.1 Any serious adverse event, or follow up to a serious adverse event, including death due to any cause other than progression of the cancer under study that occurs to any subject from the time the consent is signed through 90 days following cessation of treatment, or the initiation of new anti-cancer therapy, whichever is earlier, whether or not related to Merck product, must be reported within 5 calendar days to the MSKCC Safety Office and within 2 working days to Merck Global Safety unless specified in the ECI reporting guidance (APPENDIX C).

Non-serious Events of Clinical Interest will be forwarded to Merck Global Safety and will be handled in the same manner as SAEs.

Additionally, any serious adverse event, considered by an investigator who is a qualified physician to be related to Merck product that is brought to the attention of the investigator at any time outside of the time period specified in the previous paragraph also must be reported immediately to the Sponsor and to Merck.

SAE reports and any other relevant safety information are to be forwarded to the Merck Global Safety [contact]

A copy of all 15 Day Reports and Annual Progress Reports is submitted as required by FDA, European Union (EU), Pharmaceutical and Medical Devices agency (PMDA) or other local regulators. Investigators will cross reference this submission according to local regulations to the Merck Investigational Compound Number (IND, CSA, etc.) at the time of submission. Additionally investigators will submit a copy of these reports to Merck & Co., Inc. (Attn: Worldwide Product Safety; [contact]) at the time of submission to FDA.

All subjects with serious adverse events must be followed up for outcome.

Events of Clinical Interest

Selected non-serious and serious adverse events are also known as Events of Clinical Interest (ECI) (see APPENDIX C) and must be recorded as such on the Adverse Event case report forms/worksheets and reported within 5 calendar days to the MSKCC Safety Office and to Merck Global Safety. (Attn: Worldwide Product Safety; [contact]) according to the ECI reporting guidance (APPENDIX C).

Events of clinical interest for this trial include:

- 1. an overdose of Merck product, as defined in Section 11.1.3 Definition of an Overdose for This Protocol and Reporting of Overdose to the Sponsor, that is not associated with clinical symptoms or abnormal laboratory results.
- 2. an elevated AST or ALT lab value that is greater than or equal to 3X the upper limit of normal and an elevated total bilirubin lab value that is greater than or equal to 2X the upper limit of normal and, at the same time, an alkaline phosphatase lab value that is less than 2X the upper limit of normal, as determined by way of protocol-specified laboratory testing or unscheduled laboratory testing.
- **Note: These criteria are based upon available regulatory guidance documents. The purpose of the criteria is to specify a threshold of abnormal hepatic tests that may require an additional evaluation for an underlying etiology. The trial site guidance for assessment and follow up of these criteria can be found in the Investigator Trial File Binder (or equivalent).
- 3. In the event a subject develops any of the following AEs, a detailed narrative of the event should be reported as an ECI to the Sponsor within 5 calendar days to the

MSKCC Safety Office and to Merck Global Safety according to the ECI reporting guidance (APPENDIX C):

- a. Grade ≥ 3 diarrhea
- b. Grade ≥ 3 colitis
- c. Grade ≥ 2 pneumonitis
- d. Grade ≥ 3 hypo- or hyperthyroidism

A separate guidance document has been provided entitled "event of Clinical Interest and Immune-Related Adverse Event Guidance Document." This document provides guidance regarding identification, evaluation and management of ECIs and irAEs. Additional ECIs are identified in this guidance document and also need to be reported to the Sponsor within 5 calendar days to the MSKCC Safety Office and to Merck Global Safety according to the ECI reporting guidance (APPENDIX C).

Subjects should be assessed for possible ECIs prior to each dose. Lab results should be evaluated and subjects should be asked for signs and symptoms suggestive of an immune-related event. Subjects who develop an ECI thought to be immune-related should have additional testing to rule out other etiologic causes. If lab results or symptoms indicate a possible immune-related ECI, then additional testing should be performed to rule out other etiologic causes. If no other cause is found, then it is assumed to be immune-related.

ECIs that occur in any subject from the date of first dose through 90 days following cessation of treatment, or the initiation of a new anticancer therapy, whichever is earlier, whether or not related to the Merck"s product, must be reported within 5 calendar days to the MSKCC Safety Office and to Merck Global Safety according to the ECI reporting guidance (APPENDIX C).

